Title :Efficacy and Safety of Nadroparin Calcium-Warfarin Sequential
Anticoagulation in Portal Vein Thrombosis in Cirrhotic Patients: A
Randomized Controlled Trial

NCT number: NCT04173429

Date of the Document:2020-7-3

Statistical Analysis Plan

Statistical analysis was performed using the statistical software IBM SPSS Statistical 24.0. The analysis of the outcomes between NWS therapy group and control group was conducted by both intention-to-treat (ITT) and per-protocol (PP) analysis. All eligible patients were analyzed by ITT analysis, and patients who did not violate the protocol were analyzed by PP analysis.

Quantitative variables were expressed as the mean \pm standard deviation (SD), while qualitative variables were expressed as percentages. Quantitative variables were compared using Student's *t*-test or Wilcoxon-rank sums test, and categorical variables were compared using chi-squares or Fisher's exact test, as appropriate. Univariate and multivariate logistic regression analysis were performed to find significant end point predictors for recanalization. A two-tailed *p*-value <0.05 was considered statistically significant.

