Title :Efficacy and Safety of Nadroparin Calcium-Warfarin Sequential
Anticoagulation in Portal Vein Thrombosis in Cirrhotic Patients: A
Randomized Controlled Trial

NCT number: NCT04173429

Date of the Document:2020-7-3

Study Protocol

All patients admitted at the Gastroenterology Department of the Qilu Hospital of Shandong University in China, who were diagnosed with PVT, were prospectively and consecutively evaluated in this study. The inclusion criteria were the following: age between 18 and 75 years, liver cirrhosis diagnosis based on clinical, laboratory and imaging studies, PVT diagnosed by abdominal contrast-enhanced computed tomography (CT), contrast-enhanced magnetic resonance imaging (MRI) or portal angiography. The exclusion criteria were the following: cavernous transformation of the portal vein, uncontrolled active bleeding, platelet count lower than $10 \times 10^9/L$, creatinine more than $170 \mu\text{mol/L}$, ongoing or received antithrombotic/thrombolytic treatment, primary thrombophilia, Budd-Chiari syndrome, pregnancy or breast-feeding period, severe cardiopulmonary diseases, severe systemic infection or sepsis, and inability to sign the informed consent.

Eligible patients were randomly divided into two equal groups: NWS therapy group and control group. Randomization was performed using a computer-based random number table procedure. Randomly generated serial numbers were placed in opaque envelopes. Patients and clinicians carrying out the interventions were not blinded, while clinicians performing the imaging assessments and data analysis were blinded to the group allocation and patients' coded data.

Procedure

The NWS therapy group received a subcutaneous injection of nadroparin calcium every 12 h for 1 month followed by an oral administration of warfarin for 5 months.

Warfarin was started at least 5 days before nadroparin calcium was stopped. International normalized ratio (INR) was monitored every 3-4 days and the daily dose of warfarin was carefully adjusted by the increase or decrease of 0.75 mg until the INR target level of 2-3 was achieved. Patients in the control group did not receive any anticoagulation treatment.

All patients underwent gastroscopy to evaluate the degree of varices and received endoscopic ligation or sclerotherapy if necessary. Patients in the NWS therapy group initiated the anticoagulation therapy after endoscopic therapy.

Imaging studies

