PVT assessed by imaging examination appears as the absence of flow in part or all the lumen of the splenoportomesenteric axis, including portal vein trunk and branches, SV or SMV, with the presence of solid material in the vein. The degree (partial occlusion or complete occlusion) and extension (portal vein only or extension into the SV and/or SMV) of PVT were also evaluated in all the enrolled patients at admission by upper abdominal contrast-enhanced CT or MRI or portal angiography. The assessments of thrombosis were based on a published study(22). For each venous segment, the vein and residual patent lumen were outlined at the level of the maximum thrombosis. Total lumen area and patent lumen area were calculated with commercially available software. The degree of thrombus occlusion was estimated as a percentage by $\text{thrombosis area}/\text{total lumen area} \times 100\%$ (22). The extension of thrombosis was referred to the involved segments of the portal vein system, regardless of whether thrombosis was formed in the portal vein only or extended into the SMV and/or SV(23, 24).

Complete and partial thrombosis were defined as equal or greater than 90% and less than 90% thrombotic material presence within vessels, respectively. Although the imaging assessments were performed by a single reader, the bias is minimized as the calculated assessments are objective.

Follow-up

Follow-up visits were scheduled at the 0th and 6th month, and included clinical, laboratory and imaging evaluation. The follow-up started at the diagnosis of PVT, defined as starting on the date of the first radiological imaging documenting PVT, and stopped in January 2020 or the day of death or the date of the last visit at 6th month. Liver function and cirrhosis severity were assessed by Child-Pugh score and the Model for end-stage liver disease (MELD) score respectively at the 0th and 6th month.

Bleeding episodes were assessed every month by phone call. Once a severe bleeding episode occurred, the anticoagulation treatment was stopped immediately and endoscopic therapy was performed if necessary.

Outcomes and definitions

The primary outcome was the overall recanalization rate, both complete and partial. The secondary outcomes were bleeding rates, consisting of rates of hematemesis, melena, epistaxis, injection-site hemorrhage and other bleeding events.

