Portal vein recanalization was evaluated on the basis of imaging examination. Complete recanalization was referred to the complete disappearance of the thrombus in the portal vein trunk, at least one of the two intrahepatic portal vein branches, SMV and SV. Partial recanalization was defined as a more than 50% reduction of the thrombus,

with the thrombus not extending to other veins. No response or stable thrombosis was defined when the thrombus maintained the same dimension, or achieved a less than 50% decrease or less than 30% increase on cross section. Progression was defined as more than 30% increase of the thrombus than before or thrombus extended to unaffected segments of the splenoportomesenteric axis (Fig. 1).

Group size calculation

The overall recanalization rate of the PVT at the 6th month was chosen as the primary outcome to calculate the size of the groups. Based on previous studies (25), assuming a 30% difference in the overall recanalization of PVT at 6th month between the anticoagulation (70%) and control group (40%), 5% α and 20% β error, 27 patients were needed in each group. Considering a 10% dropout rate, 30 patients should be included in each group.

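### The stated 80% power is not delivered: it is about 57–59% by chi-square (46–48% by Fisher), mainly because 27 per group is too few, and the SAP gives no rule for patients without a month-6 image.

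*SAP*

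**What the plan says.** **Sample size (Protocol, Group size calculation).** The primary outcome is overall recanalization at month 6. The assumed rates are 70% with anticoagulation and 40% in controls, with "5% α and 20% β error". The result is 27 per group, and then: "Considering a 10% dropout rate, 30 patients should be included in each group". Allocation is 1:1: "Eligible patients were randomly divided into two equal groups: NWS therapy group and control group".

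**Test (SAP).** Categorical variables are compared by chi-square or Fisher's exact test, as appropriate. On significance: "A two-tailed *p*-value <0.05 was considered statistically significant".

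**Analysis sets (SAP).** "All eligible patients were analyzed by ITT analysis"; a per-protocol analysis covers those without protocol violations.

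**Availability of the outcome (Protocol, Follow-up).** Imaging is scheduled at months 0 and 6 only. Follow-up "stopped in January 2020 or the day of death or the date of the last visit at 6th month". Neither document gives a non-responder, imputation or completer rule for a patient who has no month-6 image.

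**The concern.** Two things do not fit together.

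First, the stated power cannot be obtained from the stated rates, significance level and group size. If the true rates were exactly those assumed, the trial would still miss the effect roughly four times in ten by chi-square, and more than half the time by Fisher. A non-significant result would then be easy to misread as evidence that anticoagulation does not help.

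Second, the 10% inflation treats dropouts as contributing nothing, so the calculation is for about 27 evaluable patients per group. The SAP's ITT analysis covers all eligible patients. A 2×2 table needs an outcome for each of them, and there is no interim image to fall back on. Without a written rule, the classification of perhaps 6 of 60 patients on the primary endpoint could be chosen after the data are seen, in a trial where patients and treating clinicians are not blinded. The power statement also cannot be tied to a definite analysis.

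**Working it through.** **Inputs.** p₁ = 0.70, p₂ = 0.40, β = 0.20, 27 then 30 per group, 10% dropout (Protocol, Group size calculation); 1:1 allocation (Protocol, Study Protocol); two-sided α = 0.05, chi-square or Fisher (SAP).

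**1. Can 27 be reproduced?** Pooled normal formula, with p̄ = (p₁ + p₂)/2:

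n = [z₁₋α/₂ √(2p̄(1−p̄)) + z₁₋β √(p₁(1−p₁) + p₂(1−p₂))]² / (p₁−p₂)²

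- p̄ = 0.55, and √(2 × 0.55 × 0.45) = √0.495 = 0.7036
- √(0.21 + 0.24) = √0.45 = 0.6708
- n = (1.960 × 0.7036 + 0.8416 × 0.6708)² / 0.09 = (1.379 + 0.565)² / 0.09 = 41.97, so **42 per group**

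Other two-sided versions give 40 (unpooled), 42 (arcsine), 44 (variance 2p̄(1−p̄) throughout) and 49 (continuity-corrected). One-sided, the pooled formula gives (1.157 + 0.565)² / 0.09 = 32.9, so 33; the other one-sided versions run from 31 to 40. None gives 27.

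**2. Dropout step.** 27/0.9 = 30, so the arithmetic is right; it is the base that fails. From 42 the same step gives 42/0.9 = 46.7, so 47.

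**3. Power at the planned size.** Normal approximation with 27 per group: z = (0.30 × √27 − 1.379)/0.6708 = (1.559 − 1.379)/0.6708 = 0.268, so power is 0.61. For exact power, every pair of success counts is enumerated and the binomial probabilities of the significant tables are summed (two-sided 0.05, Pearson chi-square without continuity correction):

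| Analysis | Rates | n per group | Normal approx. | Exact chi-square | Exact Fisher |
|---|---|---|---|---|---|
| Completers after 10% loss | 70% vs 40% | 27 | 0.61 | 0.586 | 0.481 |
| All, missing = not recanalized | 63% vs 36% | 30 | 0.55 | 0.569 | 0.462 |
| All, nobody missing | 70% vs 40% | 30 | 0.65 | 0.663 | 0.561 |

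The second row assumes 10% loss in each arm: 0.9 × 70% = 63% and 0.9 × 40% = 36%. If only one arm loses 10%, normal-approximation power at 30 per group is 43% (loss in the treatment arm only) or 76% (loss in the control arm only).

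**4. Where the shortfall comes from.** From the planned 80% to 27 completers: 80 − 58.6 = 21.4 points on the exact chi-square scale. From 27 completers to 30 with missing counted as failures: 58.6 − 56.9 = 1.7 points (about 5 by the normal approximation, 61% to 55%). The base of 27 is therefore the main cause.

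**5. Size needed under the ITT rule.** For 63% vs 36%, p̄ = 0.495 and the pooled formula gives (1.386 + 0.573)² / 0.0729 = 52.6, so 53 per group with dropouts already included. With 47 per group, exact power is 0.754 (Fisher 0.683).

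**6. What the missing rule can do to the result.** Assumed for illustration: 19/27 vs 11/27 among completers, close to the planning rates, with 3 missing per arm.

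| Rule for the missing | Table | Chi-square p | Fisher p |
|---|---|---|---|
| Left out | 19/27 vs 11/27 | 0.028 | 0.054 |
| Not recanalized | 19/30 vs 11/30 | 0.039 | 0.070 |
| Worst case for treatment | 19/30 vs 14/30 | 0.19 | 0.30 |
| Best case for treatment | 22/30 vs 11/30 | 0.004 | 0.009 |

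**The case against.** **The absence of a missing-outcome rule is only missing detail.** That is fair for the gap taken alone. In the illustration, leaving the missing out and counting them as failures lead to the same side of 0.05 under either test. Only the extreme allocations change the conclusion: the worst case loses significance by chi-square, and the best case gains it by Fisher. The power error does not depend on this gap, since 80% fails under both handlings.

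**A reader might infer that the ITT test will in practice be a completer analysis**, because the software would leave blank outcomes out of the table. The documents do not say so. The SAP says that all eligible patients are analysed, and classing the missing as not recanalized fits that sentence equally well. A completer analysis would in fact agree with the dropout step, so the two complaints cannot both apply.

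**A reader might attribute the whole gap from 80% to missing-data handling.** Step 4 shows otherwise.

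**A reader might see the January 2020 stop as a known source of missing scans and ask for it to be lifted.** No enrolment dates are given, so it may cut off nobody. Both documents are dated 3 July 2020, after that stop, so extending follow-up cannot be offered as a remedy on this evidence.

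**The calculation may have been one-sided.** The sample-size sentence does not state sidedness. But one-sided planning still needs 33 by the pooled formula, one-sided power at 27 is about 73%, and the SAP tests two-sided.

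**Conclusion.** The power statement is wrong as written. At the protocol's own rates and the SAP's two-sided 5% level, the design has about 57–59% power by chi-square and 46–48% by Fisher, against the stated 80%; about 42 evaluable patients per group would be needed. This rests on the 70% and 40% rates and, for the lower figure in each range, on equal 10% loss counted as failure. Almost all of the error lies in the base of 27.

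The dropout allowance and the ITT statement also refer to different sets of patients, and no rule connects them. That is a gap in specification. It does not show that patients will be excluded, that loss will differ by arm, or how many scans will be missing.

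**What to change.** - **Protocol, Group size calculation:** restate the power at 30 per group for the two-sided 5% test: about 59% (chi-square) or 48% (Fisher) for 27 completers per group, and about 57% or 46% for the ITT analysis at 63% vs 36%. Say which analysis and which test the figure refers to, and that 27 per group does not give 80%.
- **SAP, analysis sets:** state that the primary ITT analysis counts every randomized patient in the assigned group, and that those without month-6 imaging, for whatever reason, are classed as not recanalized.
- **SAP, sensitivity analyses:** add a completer analysis and the best- and worst-case allocations of the missing outcomes, with the number missing and the reasons by arm.

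**Cost.** A few sentences and a few extra tables, a lower stated power, and a slightly conservative primary estimate. Counting missing as failure is one of several defensible rules; the sensitivity analyses show how much depends on it.

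### If the arms are compared on Child-Pugh or MELD at month 6, adjust for the month-0 score: the SAP's unadjusted tests are valid but less precise (minor)

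*SAP*

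**What the plan says.** The protocol's Follow-up section sets two visits for the trial as a whole, with no restriction to one arm: "Follow-up visits were scheduled at the 0th and 6th month, and included clinical, laboratory and imaging evaluation". It adds that "Liver function and cirrhosis severity were assessed by Child-Pugh score" and by MELD, "score respectively at the 0th and 6th month". Each patient seen at both visits therefore has a starting value and a final value on both scores.

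The SAP's method for such measures is one general sentence: "Quantitative variables were compared using Student's" t-test or the Wilcoxon rank-sum test. It names no baseline covariate and no change score. The only regression model is logistic and serves another purpose: "Univariate and multivariate logistic regression analysis were performed to find significant end point predictors for recanalization".

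Neither score is a named outcome. Under Outcomes and definitions, "The primary outcome was the overall recanalization rate, both complete and partial", and "The secondary outcomes were bleeding rates, consisting of rates of hematemesis, melena, epistaxis, injection-site hemorrhage and other bleeding events". All of these are proportions.

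**The concern.** A patient's own starting score usually says a good deal about the score six months later. A two-sample test on month-6 values makes no use of it. The protocol describes simple randomization into two equal groups without stratification, and the groups are small, so the arms can easily start at somewhat different levels of liver disease. The design does nothing to balance the scores, and the SAP has no model that would allow for a difference.

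At stake is any statement that anticoagulation preserved or worsened liver function. Such a statement would rest on a wider confidence interval than the data allow and, in the trial actually run, on a difference that partly reflects where the arms began.

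**Working it through.** **Inputs from the documents.** The plan gives no figure for Child-Pugh or MELD, so there is none to reproduce on this point. The number of evaluable patients comes from Group size calculation: 30 recruited per group with 10% dropout, so 30 × 0.9 = 27. I use 27 only as the expected evaluable number. Whether it is enough for the primary outcome is a separate question: the usual two-sided calculation for 70% against 40% with 80% power gives 42 per group. The significance level is two-sided 5% (SAP).

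**Assumptions.** The correlation ρ between the month-0 and month-6 scores is not in the documents, so it is shown over a range of 0.3 to 0.8. I also assume normal scores, the same SD at both visits and a linear relation common to both arms. The figures are for the t-test; the rank-sum test likewise ignores the starting value, but I did not compute its loss.

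**Step 1: chance imbalance at month 0.** In SD units the difference between arms has standard error √(2/27) = 0.272.
- P(|difference| > 0.25 SD): 0.25/0.272 = 0.92, giving about 36%.
- P(|difference| > 0.50 SD): 0.50/0.272 = 1.84, giving about 7%.

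**Step 2: how much reaches month 6.** An unadjusted month-6 comparison carries ρ × imbalance. A change-score comparison over-corrects, carrying −(1 − ρ) × imbalance.

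**Step 3: precision.**
- ANCOVA variance relative to the month-6 t-test: 1 − ρ².
- ANCOVA variance relative to a change-score t-test: (1 + ρ)/2.
- Equivalent unadjusted size per arm: 27/(1 − ρ²).
- Difference detectable with 80% power, normal approximation: (1.960 + 0.842) × 0.272 = 0.76 SD unadjusted, multiplied by √(1 − ρ²) for ANCOVA.

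| ρ (assumed) | Month-6 shift from a 0.25 SD imbalance (SD) | ANCOVA / month-6 t-test variance | ANCOVA / change-score variance | 27 per arm worth | Detectable difference, ANCOVA (SD) |
|---|---|---|---|---|---|
| 0.3 | 0.075 | 0.91 | 0.65 | 30 | 0.73 |
| 0.5 | 0.125 | 0.75 | 0.75 | 36 | 0.66 |
| 0.7 | 0.175 | 0.51 | 0.85 | 53 | 0.54 |
| 0.8 | 0.200 | 0.36 | 0.90 | 75 | 0.46 |

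**Step 4: price of estimating the covariate slope.** The expected variance is inflated by 1 + 1/(2 × 27 − 4) = 1.02. The ratios to the month-6 t-test become 0.93, 0.77, 0.52 and 0.37. Simulation with 27 per arm and 20,000 runs gave 0.78, 0.52 and 0.37 at ρ = 0.5, 0.7 and 0.8. On this formula ANCOVA gains once (1 − ρ²) × 1.02 < 1, that is ρ above about √(0.02/1.02) = 0.14.

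**Step 5: validity.** In the same simulations, with no treatment effect, the unadjusted t-test rejected in 4.7% to 5.0% of all runs. Among runs with a baseline imbalance above 0.5 SD it rejected in 16%, 27% and 37% at ρ = 0.5, 0.7 and 0.8. The overall rate already includes those runs.

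**The case against.** The strongest reply is that nothing the trial set out to show depends on this. Child-Pugh and MELD appear only as follow-up assessments, no objective or hypothesis concerns them, and every listed outcome is a proportion. That stands, and it sets the rating.

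Second, the analysis criticised is not actually written down. The SAP sentence is a general default that would equally cover a baseline table. A reader might infer that the plan commits to a t-test of raw month-6 scores; the documents do not say so. They leave open month-6 values, changes, or no comparison between arms at all. If changes were tested, the starting value would be used, though not in the best way, and the gain from ANCOVA would be small at high correlations (variance ratio 0.85 or 0.90 at ρ = 0.7 or 0.8).

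Third, a reader might infer that the unadjusted test is biased, or that a baseline difference passes in full into month 6. Neither follows. Randomization keeps the test unbiased on average with type I error near 5%, and the imbalance carries over multiplied by ρ. What remains is imbalance in the one trial that is run, and a wider interval than necessary.

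Fourth, the size of the gain depends on a correlation that the documents do not give. At ρ = 0.3 the variance falls by only 9% before the cost of estimating the slope, and by about 7% after it.

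**Conclusion.** The point holds as a minor, conditional improvement. If the arms are compared on month-6 Child-Pugh or MELD, the SAP's only method for quantitative variables is valid but gives up precision and leaves chance baseline differences uncorrected. With 27 evaluable per arm, the saving in variance against a month-6 t-test runs from under 10% at ρ = 0.3 to nearly two thirds at ρ = 0.8. Against a change-score test it is 25%, 15% and 10% at ρ = 0.5, 0.7 and 0.8. These sizes rest on the assumed correlations and on equal SDs at the two visits.

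It would go too far to conclude that the recanalization or bleeding results are affected: neither uses these scores as an outcome.

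**What to change.** First state whether the arms are to be compared on Child-Pugh and MELD at all. If they are, add a sentence to the SAP: each month-6 score is compared by ANCOVA with treatment arm as factor and the month-0 value of the same score as covariate, reporting the adjusted mean difference with a 95% CI, as an exploratory analysis. Say also how deaths and missing month-6 scores are handled, since ANCOVA does not settle that. If a rank-based version is wanted for skewed scores, name it in advance instead of choosing it after seeing the data.

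The cost is one degree of freedom and a little extra analysis. Both values are already collected, so no visit or procedure changes. Timing needs care: both documents are dated 3 July 2020, while the protocol has follow-up ending by January 2020. If the sentence is added after follow-up ended, the analysis should be labelled post hoc.
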